4.3.6 RANDOMISATION

Sites must confirm in the eCRF system whether participants were randomised into the study or not. Age at randomisation will be entered in the eCRF. The randomisation procedure and access to the randomisation system is described in the trial specific procedures.

4.4 EFFICACY DATA

Participant self-report measures should ideally be completed in the absence of the caregiver.

4.4.1 MEASURE 1:COPD ASSESSMENT TEST

The COPD Assessment Test (CAT) is an eight-item health status instrument in COPD that is used to quantify the impact of COPD on the patient's health

4.4.2 MEASURE 2: EQ-5D-5L

The EQ-5D-5L²⁸ is a validated and widely used generic measure used to collection patients' health-related quality of life.

4.4.3 MEASURE 3: RESOURCE USE QUESTIONNAIRE

A resource use questionnaire²⁷ will be used to collect patients' use of primary healthcare services, social care services and out of pocket expenditure and their carers' productivity losses.

4.5 SAFETY DATA

4.5.1 SERIOUS ADVERSE EVENTS

During each assessment, participants will be asked about adverse events. All serious adverse events will be recorded in an ongoing serious adverse event log. Symptoms of disease progression need only be recorded if treatment is required or if the physician is concerned that the rate of progression is unexpected.

4.5.2 CONCOMITANT MEDICATIONS

During each assessment, participants will be asked about their current medication. All concomitant medication will be recorded in an ongoing concomitant medication log.

4.5.3 WITHDRAWAL

A withdrawal form must be completed in the event of participant death or where the participant has stopped taking study medication and is no longer prepared to provide any follow up data or have their caregiver or family doctor provide any follow up data. Where the participant has stopped study intervention but is still being followed for primary outcome data, a withdrawal form should not be completed, but a status update must be recorded in the eCRF every 3 months.

4.6 LABORATORY DATA

The results of any routine clinical blood results will be entered into the eCRF. Routine sputum antibiotic sensitivity collected data will also be stored in the eCRF at admission and at any readmission for assessment of AMR. In a sub-study of patients, stool samples will be collected at baseline prior to discharge from the index exacerbation and at 90 days to assess the effect of rescue packs on AMR rates. Assuming that the comparator group has less AMR than the intervention group, and 20% drop out, it is estimated that 34 patients from each study arm will need to be sampled and sequenced for antibiotic resistance genes (ARGs) to determine a clinically meaningful effect of rescue packs on AMR. The results of any routine nasal/throat swabs and nasal absorption will also be collected during the admission and discharge.

4.7 MEASURES TO PROMOTE PARTICIPANT RETENTION

There are no in person visits in this study and so we do not anticipate challenges with retention. We will work flexibly with patients regarding scheduling of phone calls, sending reminders before-hand.

4.8 QUALITATIVE SERVICE EVALUATION TO CHARACTERISE STANDARD-OF-CARE

Reflecting patterns in the UK¹⁰ and notwithstanding NICE guidance, standard of care in the participating sites is likely to vary greatly. Understanding the nature and level of support offered as standard of care to participants will be essential to interpretation of results. To address this need, prior to the delivery of the study described in this protocol, we will undertake a service evaluation as part of a sub-study using qualitative interviews with

relevant healthcare staff (providers and commissioners) to characterise standard of care in participating sites prior to site initiation, to identify the key aspects of variation that may have a bearing on the primary and secondary outcomes, and to inform collection of participant-level data relating to these variations in the trial. We will supplement data from these interviews with information derived from local protocols, guidance and other documents.

5. QUALITATIVE SUB-STUDY TO UNDERSTAND INTERVENTION DELIVERY

The delivery of a complex intervention with several component parts such as rescue packs and their associated interventions including education and reminders, is subject to mutation at various points in the process. This may include appropriate adaptions of the intervention to local circumstances, and changes that are likely to undermine positive impact. Both to understand the impact of the intervention (and particularly variability in impact) and to equip practitioners to make the best use of it if adopted in routine care, it is important to understand the nature of those variations and the extent to which fidelity to the intervention as intended has been achieved. We will carry out interviews after the 90-day follow-up period with patients in the study's intervention arm. We will seek a sub-sample that exhibits strong heterogeneity in characteristics that may affect participants' attitudes towards and use of rescue packs and the associated package of supporting measures.

As part of the consent process for the study, participants will be asked (optionally) to consent to being contacted by the study team regarding participation in an interview about experiences of the intervention at around 90 days. Contact details of patients who give consent to this, will be collated on a monthly basis and passed to the qualitative research team, along with basic demographic details (site, sex, age, ethnicity, language, date of discharge), to inform identification of a subsample. At follow-up calls, the research team will address eligibility for, and agreement to undertake the qualitative interviews and pass contact details on to the qualitative research team. The qualitative team will contact participants using the information provided at 90 days (+/-14 days). At this point, participants will have the chance to ask further questions about the study, and consent will be reaffirmed verbally; information sheets will be re-supplied upon request. Where a participant's preferred language is not English, this contact will be supported by a professional interpretation service. The qualitative team will keep an ongoing record of participants who agree to be interviewed, with a view to securing variation in the following characteristics and constructing a diverse sample:

- Gender
- Age
- Ethnicity
- Preferred language
- Site of recruitment

As recruitment proceeds, the profile of the sample according to each of these variables will be kept under review, and further recruitment will be targeted at groups that are less well represented in the sample to date. Up to approximately 60 participants will be recruited across all sites (around two per site on average).

Where participants agree to be interviewed, the researcher will agree an appropriate time and date for the interview. Interviews will be conducted by telephone, will take up to approximately 60 minutes, and will be audio-recorded using an encrypted device. They will follow a topic guide focusing on the participant's experience of the post-discharge intervention, including their knowledge of the use of rescue packs, whether they used a rescue pack and in what circumstances, their views on the support and guidance provided (written, telephone, and text message), and the fit of the intervention into their day-to-day lives. Topic guides informed by constructs from the COM-B framework⁴⁰ and from Burden of Treatment Theory⁴¹, with a view to understanding both the individual-level and social influences on reception and use of the rescue packs and associated support.

Following completion of interviews, audio recordings will be moved to the University of Cambridge Safe Haven storage space, and then transferred securely to a professional transcription service with appropriate confidentiality and data-sharing agreements in place. In the course of transcription, identifying features will be anonymised. Anonymised transcripts will be returned to the Safe Haven, at which point they will be checked

against audio recordings to ensure full anonymity and accuracy. Once this has been verified, audio recordings will be destroyed the anonymous transcripts will then be transferred from the University of Cambridge Safe Haven to the University of Cambridge research drive for analysis. Analysis will be based on the constant comparison approach, adapted to incorporate sensitising concepts from COM-B and Burden of Treatment theory, and will focus in particular on: (i) the impacts of participants' diverse backgrounds and circumstances on their attitudes towards and use of the rescue packs and other components of the intervention; (ii) the consequences for adherence to intended use; and (iii) the implications for refining protocols for administering rescue packs and supporting resources and how these might best be tailored to individual patients' situations.

6. Interventions

6.1 EXPLANATION FOR THE CHOICE OF COMPARATORS

The comparator is usual care, which will vary by site, and will be studied via a qualitative sub-study.

6.2 INTERVENTION AND COMPARATOR DESCRIPTION, DOSING AND LABELLING

The intervention arm consists of 3 components: i) a written (and/or translated) management plan for COPD exacerbations as per Asthma+Lung UK; ii) medication in the form of a rescue pack and iii) reminder text or telephone messages, twice per week as per section 4.1.6. A 'rescue pack' according to local prescribing guidelines, will be allocated to the intervention arm. This typically consists of 5-7 days of prednisolone (30mg to be taken once a day) and 5-7 days of amoxicillin (500mg to be taken three times a day). If participants in the intervention arm use their rescue packs a further rescue pack will be provided by the study team, up to 90 days following randomisation. The control study arm will not receive a rescue pack on randomisation, by the study team. However, participants in the control study arm may have access to rescue packs in the community, their homes or their community care team for which we will record this use on study visit telephone calls.

7. ASSIGNMENT OF INTERVENTIONS

7.1 RANDOMISATION METHOD

The method of randomisation in the trial is stratified randomisation with two stratifiers defined by COPD hospitalisations (severe exacerbation) in the last year and previous exacerbations (moderate or severe) in the last year and (excluding the index hospitalisation).

- I) Prior versus no prior severe exacerbations in the last year
- II) >=2 or <2 moderate/severe exacerbations in the last year

Randomly permuted blocks will be used within the four strata defined by the categories of these stratifiers.

Severe exacerbation is defined as a COPD exacerbation requiring hospitalisation, moderate exacerbation is defined as a COPD exacerbation that is treated with steroids and/or antibiotics, but that does not require hospitalisation.

7.2 RANDOMISATION IMPLEMENTATION

7.2.1 ALLOCATION SEQUENCE GENERATION

The randomisation sequence will be generated dynamically by the KCTU team via the KCTU web based randomisation system, in accordance with the specification agreed with the CI and Senior Statistician. The Chief Investigator, Senior Statistician and TMG will be blinded to the sequence generation.

7.2.2 ENROLMENT OF PARTICIPANTS

Participants will be enrolled in the study for the purpose of CONSORT reporting at the point of signing a consent form to being screened for eligibility and will be part of the target N=1400 at the point of randomisation.

7.2.3 ASSIGNMENT OF PARTICIPANTS TO INTERVENTIONS

Recruiting sites will assign participants to interventions by logging into the 'KCTU randomisation and IMP management system' at www.ctu.co.uk (click 'randomisation' and select 'XXXX study) and entering the participant's year of birth and age and stratifiers.

8. LABORATORIES

8.1 SAMPLE COLLECTION

In participants who provide consent, stool and nasal fluid samples for exploratory analysis will be collected at baseline prior to discharge and at 90 days. These samples will be collected by sites and in bulk will be transported for laboratory analysis to University College London (UCL) for stool and to King's College London (KCL) for nasal fluid. Samples will be stored in -20C or -80C freezers.

8.2 SAMPLE ANALYSIS PROCEDURES

All processed samples will be cell-free and not have any human genetic material. Stool samples will be analysed to understand anti-microbial resistance, including measurement of antibiotic resistance genes. Nasal fluid samples will also be analysed to measure inflammatory proteins, including chemokines and cytokines.

8.3 SAMPLE DATA RECORDING

As exploratory data, results will be recorded in a safe password controlled held spreadsheet at UCL and KCL.

8.4 SAMPLE INCIDENTS

As this is a sub-study with exploratory analysis, any incidents of sample handling or loss will not be required to be reported to the sponsor. Incidents of sampling handling or loss will be reported according to local guidelines as part of standard practice.

Sample incidents taking place at the Guy's and St Thomas' NHS Foundation Trust should also be reported on the Trust risk register Datix: http://gti.gstt.local/services/healthsafety/health-safety-main-pages/i-am-interested-in/accidents-and-incidents-reporting.aspx

9. DATA MANAGEMENT

9.1 DATA MANAGEMENT

There are two datasets in the trial: the KCTU randomisation dataset and the KCTU Elsevier Macro 4 eCRF system dataset. Source data worksheets will be supplied to all recruiting sites by the co-ordinating centre for the region. These will be prepared after the database specification is finalised and database testing is complete. Laboratory results may be reviewed directly in hospital laboratory systems where appropriate and need not be transcribed in full to the source data work. The source data worksheet must confirm that the samples were processed, and any abnormal results must be recorded and transcribed. Normal results need not be transcribed. Data will be transcribed from the source to the MACRO eCRF system, ideally within 7 days of the study visit. Participating Sites will complete source data location lists defining the source data at their site. The CI will act as custodian for the trial data. The flow of trial data is outlined in Figure 1.

§.

[figure not shown]

Figure 1. Data Flow

9.2 DATA SECURITY

Clinical trial will involve the sharing of deidentified data and samples of subjects for research purposes, both during and after the trial for the purposes of monitoring and analysis. All applicable statutory requirements and mandatory codes of practice in respect of confidentiality (including, where applicable, medical confidentiality) in relation to such trial subjects or their legal guardians. Data flow will be governed by UK-specific requirements.

Data Management Plans will be provided to the Trial Manager, detailing relevant security information about both data systems. Systems access will be strictly restricted through user-specific passwords to the authorised research team members. It is a legal requirement that passwords are not shared, and that only those authorised to access the system are allowed to do so. If new staff members join the study, a user-specific username and password must be requested and a request for access to be revoked must be requested when staff members leave the project.

Participant year of birth and age will be entered into the systems. No more identifiable data will be entered into the eCRF system. Trial sites will maintain a master participant log linking participant identifiers to study numbers. No data will be entered unless a participant has signed a consent form to participate in the trial

9.3 DATA QUALITY PROCESSES

At the database design stage, validations will be programmed into the systems to minimise data entry errors by querying the data entered in real time with sites.

The CI team will undertake appropriate reviews of the entered data, in consultation with the project analyst, where appropriate for the purpose of data cleaning and will request amendments to the MACRO eCRF system data as required. No data will be amended independently of the study site responsible for entering the data.

No data can be amended in the randomisation system, however CI or delegate (e.g., Trial Manager) may request King's Clinical Trials Unit to add notes against individual participant entries to clarify data entry errors. Any errors should be reported by site staff to the Trial Manager as soon as possible once they are detected. The trial manager will onward report errors to KCTU and retain records in the TMF.

The KCTU will provide the Trial Manager with Data Management Plans for both the Elsevier Macro eCRF system and the randomisation system once the systems are made live. Those documents will be filed in the Trial Master File.

A regular Data Management Report will be produced by KCTU and passed to the Trial Manager, who will raise Data Clarification Requests (DCRs) with sites in the eCRF system. The Trial Manager will raise DCR's. Study sites will periodically review raised DCR's and respond to the queries raised.

During site monitoring visits, the Trial Manager will raise any queries with sites via the Source Data Verification (SDV) function.

9.4 DATABASE LOCK

At the end of the trial, the site PI's will review all the data for each participant in the MACRO eCRF system and provide electronic sign-off to verify that all the data are complete and correct.

The trial manager will confirm all checks are complete and all monitors queries have been resolved prior to database lock. At this point, with the agreement of the senior statistician, all data can be formally locked for analysis.

When the final data extract is requested, KCTU will remove all data entry user access prior to data extract and will retain only 'monitor' access for site PI's and other relevant individuals.

Upon request, KCTU will provide a copy of the final exported dataset to the CI in .csv format and the CI will onward distribute to sites as appropriate. Once sites have received copies of their individual datasets and confirmation of receipt has been received, the Trial Manager will request that all user access is removed from the MACRO eCRF system. A copy of the dataset will be stored in the TMF at the end of the study.

10. SUMMARY OF KNOWN AND POTENTIAL RISK OF RESCUE PACKS

Administration of rescue packs for this study is not anticipated to induce any potential risk other than the known potential side effects as listed in the British National Formulary (BNF).

Undesirable effects of prednisolone

A wide range of psychiatric reactions including affective disorders (such as irritable, euphoric, depressed and labile mood, and suicidal thoughts), psychotic reactions (including mania, delusions, hallucinations, and aggravation of schizophrenia), behavioural disturbances, irritability, anxiety, sleep disturbances, and cognitive dysfunction including confusion and amnesia have been reported. Reactions are common and may occur in both adults and children. In adults, the frequency of severe reactions has been estimated to be 5-6%. Psychological effects have been reported on withdrawal of corticosteroids; the frequency is unknown. The

incidence of predictable undesirable effects, including hypothalamic-pituitary adrenal suppression correlates with the relative potency of the drug, dosage, timing of administration and the duration of treatment (see Section 4.4 'Special warnings and special precautions for use').

11. ADVERSE EVENT MANAGEMENT AND REPORTING

All serious adverse events will be recorded in the participants medical notes, the study source data worksheets, and the eCRF. SAE's will be additionally reported, within 24 hours of site becoming aware of the event, to KCTU.

All SAEs, SARs and SUSARs (except those specified in this protocol as not requiring reporting) will be reported immediately (and certainly no later than 24hrs) as per the instructions on the SAE report form.

In research other than CTIMPs, a Serious Adverse Event (SAE), Serious Adverse Reaction (SAR) or Suspected Unexpected Serious Adverse Reaction (SUSAR) is defined as any adverse event, adverse reaction or unexpected adverse reaction, respectively, that:

- o results in death
- o is life-threatening
- o required hospitalisation or prolongation of existing hospitalisation
- o results in persistent or significant disability or incapacity
- o consists of a congenital anomaly or birth defect
- o is otherwise considered medically significant by the investigator

An SAE occurring to a research participant should be reported to the main REC (the REC that gave favourable opinion of the study) where in the opinion of the Chief/Principal Investigator the event was:

- o "Related" that is, it resulted from administration of any of the research procedures, and
- o "unexpected" that is, the type of event is not listed in the protocol (section10)/BNF as an expected occurrence.

The Chief/Principal Investigator or Sponsor must submit reports of related and unexpected SAEs within 15 days of the Chief/Principal Investigator becoming aware of the event, using the SAE report form for non-CTIMPs available from: https://www.hra.nhs.uk/approvals-amendments/managing-your-approval/safety-reporting/

Important Medical Events (IME) & Pregnancy: Events that may not be immediately life-threatening or result in death or hospitalisation but may jeopardise the participant or may require intervention to prevent one of the other outcomes listed in the definition above should also be considered serious. Although not a serious adverse event, any unplanned pregnancy will also be reported via the SAE reporting system.

11.1 EVALUATING SAES

11.1.1 ASSESSMENT OF INTENSITY

The Investigator will make an assessment of intensity for each SAE reported during the study. The assessment will be based on the Investigator's clinical judgement. The intensity of each SAE recorded in the eCRF should be assigned to one of the following categories:

- o Mild; An event that is easily tolerated by the participant, causing minimal discomfort and not interfering with everyday activities
- o Moderate; An event that is sufficiently discomforting to interfere with normal everyday activities
- Severe; An event, which is incapacitating and prevents normal everyday activities

An AE that is assessed as severe should not be confused with an SAE. Severity is a category utilised for rating the intensity of an event; and both AEs and SAEs can be assessed as severe.

11.1.2 ASSESSMENT OF CAUSALITY

The Investigator is obligated to assess the relationship between intervention and the occurrence of each SAE. The Investigator will use clinical judgment to determine the relationship. Alternative causes, such as natural history of the underlying diseases, concomitant therapy, other risk factors, and the temporal relationship of the event to the investigational product will be considered and investigated.

The causal relationship to the study procedures assessed by the Investigator (or medically qualified delegate) should be assessed using the following classifications:

- o Not Related: In the Investigator's opinion, there is not a causal relationship between the study intervention and the SAE.
- O Unlikely: The temporal association between the SAE and study internevtion is such that the study intervention is not likely to have any reasonable association with the SAE.
- Possible: The SAE could have been caused by the study participant's clinical state or the study intervention.
- Likely: The SAE follows a reasonable temporal sequence from the time of study intervention administration, abates upon discontinuation of the study intervention and cannot be reasonably explained by the known characteristics of the study participant's clinical state.
- o Definitely: The SAE follows a reasonable temporal sequence from the time of study intervention administration or reappears when study interventionis reintroduced.

There may be situations when an SAE has occurred, and the Investigator has minimal information to include in the initial report to the Sponsor. However, it is very important that the Investigator always assesses causality for every event prior to transmission of the SAE form to the Sponsor. The Investigator may change his/her opinion of causality considering follow-up information, amending the SAE form accordingly. The causality assessment is one of the criteria used when determining regulatory reporting requirements.

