4.1.6 TWICE WEEKLY TEXT MESSAGING/TELEPHONE

In the intervention arm, Patients will receive twice weekly telephone calls or text messages for 90 days following randomisation. This will ask patients about their level of symptoms and remind patients that if there is a sustained increase in their symptoms consistent with an exacerbation, to use their education plan, consider using their rescue pack and to contact their usual clinical provider.

Frequent repeated patient contact is believed to lead to

- •Earlier recognition of symptoms
- •Earlier intervention by appropriate use of rescue pack
- •Reduced severity of exacerbation

- •Reduced rate of readmission
- Earlier recognition of signs of exacerbation and knowledge of appropriate action

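### As worded, the top SAE causality grade (Definitely) can be met on timing alone, so it demands less evidence than the grade below it (Likely)

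*Protocol*

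**What the plan says.** Protocol section 11.1.2 sets out five causality grades for SAEs, rising from *Not Related* through *Unlikely*, *Possible* and *Likely* to *Definitely*. The last three matter here.

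- *Possible*: "Possible: The SAE could have been caused by the study participant's clinical state or the study intervention".
- *Likely* begins "Likely: The SAE follows a reasonable temporal sequence from the time of study intervention administration" and then adds two further conditions, that the event "abates upon discontinuation of the study intervention and cannot be reasonably explained by the known characteristics of the study participant's clinical state".
- *Definitely*: "Definitely: The SAE follows a reasonable temporal sequence from the time of study intervention administration or reappears when study interventionis reintroduced".

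The same section says of the investigator's assessment: "The Investigator will use clinical judgment to determine the relationship". It also asks that other causes, including the natural course of the underlying disease, be considered and investigated. On the use of the grade it says: "The causality assessment is one of the criteria used when determining regulatory reporting requirements".

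Three other parts of the protocol bear on the point. Section 11 counts hospitalisation as an SAE. Section 11.1.6 makes SAEs leading to hospitalisation within 90 days a data source for the primary endpoint. Section 4.1.6 describes a prolonged intervention: "Patients will receive twice weekly telephone calls or text messages for 90 days following randomisation". Section 4.1.3 has the rescue pack handed over before discharge.

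**The concern.** A graded causality scale works only if each step up requires at least as much evidence as the step below. Here the last step goes the other way. *Likely* requires the assessor to have excluded the participant's clinical state as a reasonable explanation. *Definitely* drops that requirement, and drops abatement too, as long as the timing fits.

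Timing carries little information in this trial. The intervention starts at or before discharge and continues for 90 days, so readmissions in that window come after it has begun. Participants are prompted to consider the pack when symptoms worsen (section 4.1.6), so an exacerbation already under way may lead first to pack use and then to admission. The condition that would separate disease from intervention in such a case is the one missing from the top grade.

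What is at stake is whether SAE causality grades mean the same thing across sites. A site applying the written definition and a site relying on the general instruction about alternative causes could grade the same readmission at opposite ends of the scale. Controls receive no study pack and the messages are for the intervention arm only, so the problem can arise in one arm only. The trial is open label, so assessors know the arm.

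**Working it through.** **1. The two definitions side by side**

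| Element | *Likely* | *Definitely* |
|---|---|---|
| T: reasonable temporal sequence | required | sufficient alone |
| A: abates on discontinuation | required | not mentioned |
| N: not reasonably explained by clinical state | required | not mentioned |
| R: reappears on reintroduction | not mentioned | sufficient alone |

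In logical form, *Likely* = T and A and N; *Definitely* = T or R.

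**2. Enumeration.** Four yes/no elements give 2 × 2 × 2 × 2 = 16 combinations.

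- *Likely* fixes T, A and N and leaves R free: 2 of 16.
- *Definitely* fails only when T and R are both absent, which is 4 combinations: 16 − 4 = 12 of 16.
- Both *Likely* combinations have T present, so both also satisfy *Definitely*. The reverse is false for the other 10.

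The set meeting *Likely* therefore lies strictly inside the set meeting *Definitely*. On a properly ordered scale the containment runs the other way. If *Definitely* were T and A and N and R, 1 of 16 would meet it, and that one would lie inside *Likely*.

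**3. A concrete case.** Take a readmission after the intervention has started that the participant's COPD explains: T present, N absent. *Likely* fails because N fails. *Definitely* is met because T holds. *Possible* also fits.

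**4. How many events could be touched.** Inputs from section 13.3: readmission 43% (control) and 34.4% (intervention), 515 events, 90% power, two-sided 5%, 1:1 allocation, 1331 analysed, 1400 randomised.

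The plan's own figures reproduce:

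- Hazard ratio = ln(1 − 0.344) / ln(1 − 0.43) = 0.750.
- Freedman's formula at 90% power gives 515 events, as stated (Schoenfeld's gives 508).
- N = 515 / ((0.43 + 0.344) / 2) = 515 / 0.387 = 1330.7, so 1331.
- Allowing for 5% withdrawal, 1331 / 0.95 = 1401.1, or 1402 for equal arms, against the stated 1400.

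Intervention-arm participants with a first readmission within 90 days at the planned rate:

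- Analysed: 1331 / 2 = 665.5; 665.5 × 0.344 = 228.9, about 229.
- Randomised: 1400 / 2 = 700; 700 × 0.344 = 240.8, about 241.

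These are simply the planned intervention-arm readmission counts. They equal the number meeting T only if every readmission, for any cause and at any time in the window, counts as being in reasonable temporal sequence from administration. The protocol defines neither term; administration could mean the pack being handed over, the pack being taken, or a message being sent. So 229 to 241 is a ceiling, and the protocol gives no basis for a lower figure.

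**The case against.** The strongest reply is that the definitions do not stand alone. Section 11.1.2 puts clinical judgement over all five grades and requires other causes, the underlying disease among them, to be considered. *Not Related* rests on the investigator's opinion, and *Possible* expressly covers an event that the participant's clinical state could have caused. A sensible investigator would put a COPD readmission in one of those. This stands as a limit on the harm. It does not put the scale in order, because judgement still has to be expressed through categories whose top two are in the wrong order.

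A reader might infer more than the protocol supports:

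- **That ordinary readmissions will be graded *Definitely*, about 229 to 241 of them.** The wording permits that grade, but the surrounding text points away from it, and the count is a ceiling.
- **That the grade decides which SAEs go to the REC.** Section 11 has its own test: in the investigator's opinion the event resulted from the research procedures and was also unexpected. Nothing maps the five grades onto that test. Section 11.1.3 adds that a reasonable possibility needs facts, evidence or arguments. Section 11.1.2 calls causality only one of the reporting criteria.
- **That trial results depend on it.** Section 13.2 lists serious adverse events without reference to relatedness. Section 11.2 has relevant adverse events reported to the DMC and does not mention causality grades. The primary outcome is all-cause. Section 11.1.6 uses SAE forms to establish whether a hospitalisation was COPD-related, which is a different question from whether the intervention caused it.

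**Conclusion.** The definition is wrong as written. Timing alone satisfies *Definitely*, while *Likely* requires timing together with two further conditions, so the highest grade is the less demanding of the two. This follows from the text alone and needs no outside assumption.

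The practical size is bounded. At most about 229 to 241 intervention-arm participants would have a first readmission that could meet the timing condition, assuming the planned 34.4% rate, 1:1 allocation, and the broadest reading of the two undefined terms. How many would actually be graded that way cannot be derived from the protocol.

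The consequence is limited to the consistency of SAE causality grading and its part in reporting decisions. The log-rank test of all-cause readmission does not use the grade and is unaffected. This is a wording defect in the safety section that should be corrected; it does not threaten the trial's main result.

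**What to change.** Reword *Definitely* in section 11.1.2 so that it contains every condition of *Likely* in the same words (temporal sequence, abatement on discontinuation, no reasonable explanation in the participant's clinical state) **and** adds further evidence, such as reappearance on reintroduction. If abatement is to be qualified for events where it cannot be judged, the qualifier must appear in both grades. If only *Definitely* carried it, an event could still meet *Definitely* while failing *Likely*, and part of the inversion would remain.

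Make the same change on the SAE form if it repeats the wording, notify sites, and re-rate any SAE already graded *Definitely*. The cost is one sentence in the protocol, a possible form update, a site notice and that re-rating. Visits, data items, sample size and the primary analysis do not change.
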